4.2 Puffing Topography

An intended sample size of 12 subjects in each of the two groups who switch from smoking usual brand to VLN cigarettes has been set for this study. This is based on powering the primary objective of a within-group comparison of puffing topography parameters at baseline and end-of-study. The calculation was based on the number of pairs required to perform a two-tailed paired t-test with 80% power and an alpha level of 0.05 to detect significant differences between UB and VLN cigarettes and is based on available puffing topography data (5). This sample size will also provide sufficient power to detect differences in nicotine PK between UB and VLN cigarettes.

5. ANALYSIS POPULATIONS

The statistical analysis will be based on separate, hierarchically organized, analysis populations defined as the following:

Safety population: All enrolled subjects who smoked at least one cigarette of any type. This population will be used for safety analysis.

Intent-to-treat (ITT) population: All subjects who had at least one valid recording of cigarette consumption (a period of one week of >70% completion of their e-diary).

Per-protocol (PP) population: All subjects who had valid recording of cigarette consumption and completed the study according to the protocol. Data will be excluded from this population:

- If a subject self-reports smoking a significant number of cigarettes other than those which they have been assigned according to the protocol, or if this is apparent following checking of their collected used cigarette butts
- If there is a significant discrepancy between the self-reported number of cigarettes smoked per day and the number of used cigarette butts collected
- If a subject is non-compliant based on a published method of assessing compliance. After switching, subjects will be deemed non-compliant if their ratio of [plasma cotinine/CPD VLN]/[plasma cotinine/CPD baseline] exceeds 0.2.

If it is determined that a subject is pregnant during the study, the pregnant subject's data will be listed but excluded from all PK parameter summaries.

PK Population: Subjects in the PP or ITT population who have at least one PK blood draw resulting in at least one quantifiable plasma nicotine concentration. This population will be used for PK analysis (secondary endpoint analysis) and all available data will be included in the concentration and PK parameter tables to the extent possible.

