5.10 Product Trial

At screening, subjects will have an opportunity to smoke 2-3 VLN cigarettes over a 1-hour period to ensure that they can tolerate smoking those cigarettes for a period of 6 weeks. The number of cigarettes smoked will be documented, as will any abnormal events (e.g., excessive coughing) during the product trial. Subjects who react negatively (*i.e.*, unwilling to use and/or cannot tolerate the product [experience adverse events (AEs) that will prevent them from continuing to use the product as judged by the Investigator]) to the VLN cigarettes during the product trial period will not continue in the study.

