5.12.11.2 Reporting

All AEs occurring during this clinical trial after the subject has used study products (including the product trial at Screening) must be recorded on the CRF, including the date and time of onset, action taken, outcome (resolved, improved, unchanged, worse, fatal, or unknown/lost to follow-up), duration, relationship to product administration, and severity for each event. AEs will be coded using most current version of the Medical Dictionary for Regulatory Activities (MedDRA[®]) available at Celerion.

Events captured between Screening until the first product use (Product Trial) will be documented as baseline signs and symptoms.

The Investigator will review each event and assess its relationship to product administration as unrelated, unlikely, possibly, probably, or likely.

In addition, each sign or symptom reported will be graded on a 3-point severity scale using mild, moderate, or severe.

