6.2 Analysis Populations

The statistical analysis will be based on separate, hierarchically organised, analysis populations defined as the following:

Safety population. All subjects who smoked at least one VLN cigarette

Intent-to-treat (ITT) population. All subjects who had at least one valid recording of cigarette consumption (a period of one week of >70% completion of their e-diary).

Per-protocol (PP) population. All subjects who had valid recording of cigarette consumption and completed the study according to the protocol. Data will be excluded from this population:

- If a subject self-reports smoking a significant number of cigarettes other than those which they have been assigned according to the protocol, or if this is apparent following checking of their collected used cigarette butts
- If there is a significant discrepancy between the self-reported number of cigarettes smoked per day and the number of used cigarette butts collected
- Based on a published method of assessing compliance (6). After switching, subjects will be deemed non-compliant if their ratio of [plasma cotinine/CPD VLN]/[plasma cotinine/CPD baseline] exceeds 0.2.

If it is determined that a subject is pregnant during the study, the pregnant subject's data will be listed but excluded from all PK parameter summaries.

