12. SUMMARY OF CHANGES FROM PROTOCOL-PLANNED ANALYSIS

The analyses described in this SAP are aligned with those analyses described in the protocol.

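### The SAP's Safety population requires enrolment, so people who smoked VLN at the screening product trial but were never enrolled fall outside every planned AE and SAE table, and SAP 12 declares no change

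*SAP*

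**What the plan says.** Protocol 6.2 defines the Safety population as "All subjects who smoked at least one VLN cigarette", with no enrolment condition. SAP 5 defines it as "All enrolled subjects who smoked at least one cigarette of any type" and adds: "This population will be used for safety analysis".

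VLN exposure starts before enrolment. Protocol 5.10 states: "At screening, subjects will have an opportunity to smoke 2-3 VLN cigarettes over a 1-hour period". A person who is unwilling to use the product, or who has AEs that prevent further use, is stopped there: those who react negatively "to the VLN cigarettes during the product trial period will not continue in the study".

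The protocol treats that exposure as reportable. Protocol 5.12.11.2 reads: "All AEs occurring during this clinical trial after the subject has used study products (including the product trial at Screening) must be recorded". Protocol 6.4 dates product-use-emergent AEs from the first study product use and names the Product Trial as that use.

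SAP 12, the place for departures from the protocol, says only: "The analyses described in this SAP are aligned with those analyses described in the protocol".

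**The concern.** A safety set should contain everyone exposed to the investigational product. Here some VLN-exposed people are left out, and for part of them the reason is an AE on VLN. The planned AE tables would then describe tolerability in a group from which people who could not tolerate the product at first use had already been removed. A reader of the study report would not see this, because the SAP describes its analyses as aligned with the protocol. AEs are the only safety endpoint named in protocol 2.2 and SAP 2.4, so these tables carry the safety reporting.

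**Working it through.** The plan gives no figure to reproduce. The check is who is exposed, when enrolment happens, and which population each output uses.

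**1. When does enrolment happen?** Neither document defines it. Three places agree that it follows screening:
- Protocol 2.1 and SAP 3 have 70 + 70 = 140 smokers enrolled and starting at Week -1, after screening procedures that include the product trial.
- Protocol 3.4 gives a screening number first and a definitive subject number on enrolment.
- SAP 13.3 has a separate discontinuation listing for screen failures (Appendix 16.2.1.2).

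**2. Who falls in which set?**

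| Person | Smoked VLN | Enrolled | Protocol 6.2 set | SAP 5 set |
|---|---|---|---|---|
| Tried VLN, went on to Week -1 | yes | yes | in | in |
| Tried VLN, stopped because of an AE | yes | no | in | out |
| Tried VLN, unwilling to use it | yes | no | in | out |
| Tried VLN without difficulty, screened out for another reason or did not return | yes | no | in | out |

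The last row arises because the trial is one of many screening procedures (protocol 5.1). A laboratory, ECG, serology or drug-screen result can exclude someone who has already smoked VLN.

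The SAP's phrase 'of any type' changes little, since enrolled subjects are expected to have come through the VLN trial in either arm. The operative word is 'enrolled'.

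**3. Which outputs use the SAP set?** In SAP 13.1 to 13.3, these are all titled for the Safety population:
- AE and SAE tables: 12-1, 14.3.1.1, 14.3.1.2, 14.3.1.3 and 14.3.2.1, that is 5 of 5.
- The AE listing, Appendix 16.2.7.1.
- The VLN product-trial listing, Appendix 16.2.5.2.1.

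A never-enrolled trialler has a place only in Appendix 16.2.1.2. Its shell in SAP 15 holds site, subject number, date, reason and a free-text specification, with no AE fields.

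**4. Is there a column for product-trial AEs?** The shells for Tables 12-1 and 14.3.1.1 have a Baseline column (Week -1, usual brand), four product groups, and an Overall column that counts AEs only from the start of Week 1. Product-trial AEs have no clear column even for enrolled subjects. Changing the population definition alone would therefore not display them.

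**5. Size.** The documents give no product-trial failure rate. Let *d* be an assumed share of otherwise eligible triallers stopped at the trial. With 140 enrolled, the number stopped is 140 × d / (1 − d), rounded up:

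| Assumed d | 140 × d / (1 − d) | People |
|---|---|---|
| 2% | 2.9 | 3 |
| 5% | 7.4 | 8 |
| 10% | 15.6 | 16 |
| 15% | 24.7 | 25 |
| 20% | 35.0 | 35 |

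This counts only product-trial failures. It omits triallers screened out for other reasons, and it says nothing about how many had an AE.

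**The case against.** The strongest case on the other side has four parts.

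**The SAP may change the plan.** The opening of protocol 6 allows this and requires an amendment only for major changes to the primary endpoints or their analysis. That is correct, so the departure is permitted. What is missing is disclosure, because SAP 12 denies any difference.

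**Screen failures are normally left out.** That is usual when screening involves no exposure. Here people smoke the investigational product under the protocol, and the protocol's own definition takes them in.

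**The data are kept.** Protocol 9.1 provides CRFs for each screened subject, and SAP 11.4 says all AEs in the database will be listed. A reader might infer from the population definition that these AEs are simply discarded. The documents do not go that far: on listings the SAP contradicts itself, since its only AE listing is restricted to the Safety population. The promise in SAP 11.4 does not reach the tables.

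**Importance is limited.** No primary or secondary objective concerns safety, and no consumption, topography, biomarker, PK or subjective result changes. This stands.

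Two stronger readings are tempting and should be resisted. One is that the SAP set equals the protocol set minus product-trial failures; in fact it also loses VLN-exposed people excluded for unrelated reasons. The other is that those lost have AEs by definition. That holds only for people stopped for intolerance, because protocol 5.10 also counts mere unwillingness as a negative reaction.

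**Conclusion.** The concern stands as an undeclared narrowing of the Safety population, together with the lack of any AE output for people who tried VLN and were not enrolled. It rests on reading 'enrolled' as a step after screening. That is an inference, but every relevant place in the two documents supports it.

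The number of people affected and their AE rate are not in the documents. The range of 3 to 35 follows from assumed failure rates and is no estimate. Nor can the net effect on a reported AE percentage be determined. Leaving out those stopped for AEs removes people who all had one, but leaving out the unwilling and those excluded for other reasons removes people who may have had none. What can be said is that some exclusions depend on the safety outcome and that the planned tables cannot show how many.

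**What to change.** For the AE and SAE outputs, use the protocol set: all subjects who smoked at least one VLN cigarette, including at the product trial. Add a separate product-trial column or table, and a listing covering all triallers. Give the number who tried VLN, the number with an AE, and the number stopped because of an AE. Bring the AE listing into line with SAP 11.4.

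The enrolled set may stay for the by-group disposition, demographic, laboratory and vital-sign tables, because people never assigned have no product group to be shown under. State that difference from the protocol in SAP 12.

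The cost is SAP wording plus one additional AE table or column and one listing. No new data are needed, since the protocol already requires these AEs to be recorded and provides CRFs for each screened subject.

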5.1 Preliminary Analyses

Topline preliminary reports will be prepared using final PK and puffing topography data. The PK and puffing topography TFLs listed in [Section 13](#) will be included in the topline reports.

6. PRODUCT DESCRIPTION

The following investigational products will be used during this study:

Product	Short Description	Long Description
Non-mentholated VLN cigarette	VLN non-mentholated	Non-mentholated VLN cigarettes
Mentholated VLN cigarette	VLN mentholated	Mentholated VLN cigarettes
UB non-mentholated cigarette	UB non-mentholated	Subjects' UB non-mentholated filtered cigarettes
UB mentholated cigarette	UB mentholated	Subjects' UB mentholated filtered cigarettes

For the PK and safety text and analysis, table and listing headers, and AE (on rare occasion this may also apply to additional safety endpoints), the product will be described using the short description.

For figures, listings, and footnotes, the long description will be used, wherever feasible.

7. PRODUCT USE

7.1 Product Use Measurements and Collection Schedule

7.1.1 Product Use History

Subjects will be required to report previous tobacco- and nicotine-product use histories to satisfy the study inclusion and exclusion criteria. In addition, the subject will be asked if he/she is planning to quit smoking within the next 3 months. Those planning to quit will be excluded from participating in the study.

The subjects' tobacco use and smoking history (including a color photocopy of their UB cigarette package along with a ruler) will be recorded at Screening. Verification of the subject's UB cigarette brand will be made at the end of Week -1 clinic visit.

7.1.2 Product Use Recording

Subjects will be provided with e-diaries to record their daily cigarette consumption, both when in clinical confinement during study visits and during ambulatory periods. Subjects will be instructed to record both compliant and non-compliant (if any) daily numbers of cigarettes smoked. Non-compliant consumption in the subjects randomized to smoke VLN cigarettes is defined as nicotine product consumption other than their UB cigarettes during the baseline period (Week -1) or VLN cigarettes following switching (Weeks 1 to 6). Non-compliant consumption in the subjects randomized to continue to smoke their UB cigarettes is defined as nicotine product consumption other than their UB cigarettes between Week -1 and Week 6. For the purposes of data analysis, the e-diary record of cigarette consumption will be used as the primary variable.

Subjects will be provided with metal canisters in which to store their used cigarette butts during the ambulatory study periods. This is for the purposes of assessing both compliance with the study requirements and the accuracy of their self-reported (electronic diary) cigarette consumption. Subjects will be requested to collect butts of all cigarettes smoked, both compliant and non-compliant.

At the end of each collection period, the total number of butts in the canisters for the whole of that period will be counted and recorded. The number of each type of cigarette (study cigarette and non-study cigarette) will also be recorded. The cigarette butt count will be reconciled against that subject's e-diary record of cigarette consumption.

7.1.3 Puffing Topography

At clinic visits at the end of Weeks -1, 2 and 6, a randomly-selected subset of 18 non-menthol and 18 menthol smoker subjects will complete a puffing topography evaluation session with either their UB (Week -1) or the VLN (Weeks 2 and 6) cigarettes. These subjects will be/have been assigned to switch to smoking VLN cigarettes. These assessments will only be performed at a single clinical site (Lincoln) and will take place during the 24-hour confinement period.

During the puffing topography assessment, subjects will engage in a 1 hour ad libitum smoking session with their UB (Week -1) or the VLN (Weeks 2 and 6) cigarettes. In these sessions, subjects will smoke cigarettes with the mobile smoking puff analyzer (SPA-M; Sodim). The topography device will be monitored to ensure the device is actively recording during each session.

Topography assessments will be started at least one hour following either the subject's breakfast or lunch. The puffing topography session for each subject at Weeks 2 and 6 should be within \pm 2 hours of the time of their Week -1 session. Additional details and instructions for puffing topography procedures will be provided separately.

The following topography parameters will be assessed:

- Puff duration
- Puff volume
- Peak puff flow rate
- Average flow rate
- Inter-puff interval

7.2 Data Summarization and Presentation of Primary Endpoints

Study product use (study product, CPD and cigarette butts) will be listed by subject and study week. CPD and cigarette butts will be summarized by study week and study product using descriptive statistics (number of observations [n], arithmetic mean [Mean], standard deviation [SD], coefficient of variation [CV%], standard error of the mean [SEM], minimum, median, and maximum). The total duration of the product use (sum of the duration of each product use) will also be summarized. The descriptive statistics will be presented for both PP and ITT populations.

Topography parameters (puff duration, puff volume, peak puff flow rate, average flow rate, and inter-puff interval) will be listed by subject and summarized by study product and time point (Week -1, 2, or 6).

7.3 Statistical Analysis of Primary Endpoints

Paired t-tests will be used to compare cigarette consumption (CPD) and puffing topography parameters at the Week 2 and Week 6 time points with the baseline (Week -1) values. This analysis will be conducted on the evaluable subjects in the PP population. If data are unexpectedly found not to be normally distributed, an appropriate non-parametric test will be performed. Differences will be considered statistically significant at an alpha level of 0.05. Means, difference of means, 90% confidence interval for difference, and p-value will be presented.

The following SAS codes will be used for the analysis:

```
Proc ttest data=<>;  
By product_group;  
Paired week_X*baseline;  
Run;
```

Where week_X will be either Week 2 or Week 6. Product Groups are VLN non-mentholated, VLN non-mentholated, and VLN combined which pooled non-mentholated and mentholated groups. The primary analysis will be based on the VLN combined product group.

In addition, a linear mixed model analysis of variance will be used to compare the between product group differences in the absolute change from baseline values of the consumption and puffing topography parameters. Product group, week, and product group by week interaction will be the fixed factors in the model. A restricted maximum likelihood estimation method with an unstructured (UN) covariance structure will be applied. If the model does not converge, the first order autoregressive AR(1) and/or compound symmetry CS covariance structures will be tested as alternatives. The least-square mean difference, 95% confidence interval and p-value will be provided for the product group difference. The pairwise comparisons (VLN non-mentholated versus UB non-mentholated, VLN mentholated versus UB mentholated, and VLN combined versus UB combined) will be performed at week Week 2 and Week 6. Least-square means (LSMeans), difference of LSMeans, 90% confidence interval for difference, and p-value for difference will be presented.

The following SAS codes will be used to perform the analysis.

```
Proc mixed data=<>;  
Class subject product_group week;  
Model response = product_group week product_group*week /ddf=kr;  
Repeated week/type=<type> subject=subject;  
LSmeans product_group*week/CL alpha=0.05 CL pdiff;  
Run;
```

The primary analysis will be the pairwise comparisons of VLN combined versus UB combined (pooled non-mentholated and mentholated groups).

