6.1 Sample Size Estimation

6.1.1 Cigarette consumption

An intended sample size of 50 subjects in each of the two groups who switch from smoking usual brand to VLN cigarettes has been set for this study. This is based on powering the primary objective of a within-group comparison of cigarette consumption at baseline and end-of-study. The calculation was based on the number of pairs required to perform a two-tailed paired t-test with 80% power and an alpha level of 0.05 for a decrease in cigarette consumption of 3 CPD compared to available historical consumption data (2, 4). The sample size was determined to be adequate based on potential non-compliance with the use of VLN cigarettes (2). A lower number (20) of smokers will be randomized to the continue-to-smoke usual brand groups, given the lower variability in consumption data and lower non-compliance anticipated in these groups. This will provide sufficient power for the secondary objective of between-group comparisons in cigarette consumption.

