6.3.7 Statistical Methods for the Primary Endpoints

Paired t-tests will be used to compare cigarette consumption (CPD) and puffing topography parameters at the Week 2 and 6 time points with the baseline (Week -1) values. This analysis will be conducted on the evaluable subjects in the PP population. If data are unexpectedly found not to be normally distributed, an appropriate non-parametric test will be performed. Differences will be considered statistically significant at an alpha level of 0.05.

In addition, a linear mixed model analysis of variance will be used to compare the between-cohort differences in the absolute change from baseline values of the consumption and puffing topography parameters.

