13.1 In-text Summary Tables and Figures

The following is a list of table and figure titles that will be included in the text of the CSR. Tables and figures will be numbered appropriately during compilation of the CSR.

Section 10:

Table 10-1 Subject Disposition Summary (Safety and PP population)

Section 11:

Table 11-1 Demographic and Smoking History Summary (Safety and PP population)

Table 11-2 Summary of Number of Cigarettes Smoked per Week by Study Product Group and Study Week (PP Population)

Table 11-3 Statistical Comparison of Number of Cigarettes Smoked per Week at Weeks 2 and 6 Versus Week -1 by Study Product Group (PP Population)

Table 11-4 Summary of Puffing Topography Parameters by Study Product Group and Study Week (PP Population)

Table 11-5 Statistical Comparison of Puffing Topography Parameters at Weeks 2 and 6 Versus Week -1 by Study Product Group (PP Population)

Table 11-6 Summary of Urinary NNAL Mass Excreted (unit) by Study Product Group and Study Week (PP Population)

Table 11-7 Statistical Comparison of Urinary NNAL Mass Excreted (unit) at Weeks 2 and 6 Versus Week -1 by Study Product Group (PP Population)

Table 11-8 Summary of Urinary NNN Mass Excreted (unit) by Study Product Group and Study Week (PP Population)

Table 11-9 Statistical Comparison of Urinary NNN Mass Excreted (unit) at Weeks 2 and 6 Versus Week -1 by Study Product Group (PP Population)

Table 11-10 Summary of Urinary 3-HPMA Mass Excreted (unit) by Study Product Group and Study Week (PP Population)

Table 11-11 Statistical Comparison of Urinary 3-HPMA Mass Excreted (unit) at Weeks 2 and 6 Versus Week -1 by Study Product Group (PP Population)

Table 11-12 Summary of Urinary S-PMA Mass Excreted (unit) by Study Product Group and Study Week (PP Population)

Table 11-13 Statistical Comparison of Urinary S-PMA Mass Excreted (unit) at Weeks 2 and 6 Versus Week -1 by Study Product Group (PP Population)

Table 11-14 Summary of Urinary 1-OHP Mass Excreted (unit) by Study Product Group and Study Week (PP Population)

Table 11-15 Statistical Comparison of Urinary 1-OHP Mass Excreted (unit) at Weeks 2 and 6 Versus Week -1 by Study Product Group (PP Population)

Table 11-16 Summary of Urinary Tneq Mass Excreted (unit) by Study Product Group and Study Week (PP Population)

Table 11-17 Statistical Comparison of Urinary Tneq Mass Excreted (unit) at Weeks 2 and 6 Versus Week -1 by Study Product Group (PP Population)

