		SD	XX.XX	XX.XX	XX.XX	XX.XX	XX.XX
		Minimum	XX	XX	XX	XX	XX
		Median	XX.X	XX.X	XX.X	XX.X	XX.X

Population	Trait	Category/Statistics	VLN Non-Mentholated	VLN Mentholated	UB Non-Mentholated	UN Mentholated	Overall			
			XX	XX	XX	XX				
BMI = Body mass index, CPD = Cigarettes per day Age is calculated at the date of the informed consent. UB non-mentholated = Subjects' UB non-mentholated filtered cigarettes UB mentholated = Subjects' UB mentholated filtered cigarettes VLN non-mentholated = Non-mentholated VLN cigarettes VLN mentholated = Mentholated VLN cigarettes										
Source: Tables 14.1.2 and 14.1.3 Program: /CAXXXX/sas_prg/stsas/intexttest/t_dem.sas DDMMYY YYYY HH:MM										

Programmer Note: ITT and PP population will also be presented in the table.

In-text Table 11-2 will be in the following format:

Table 11-2 Summary of Number of Cigarettes Smoked per Week by Study Product Group and Study Week (PP Population)

Study Week	Statistics	VLN Non-Menthолated	VLN Mentholated	UB Non-Menthолated	UB Mentholated
Week -1*	n	X	X	X	X
	Mean (SD)	XX.X (XX.XX)	XX.X (XX.XX)	XX.X (XX.XX)	XX.X (XX.XX)
	Median	XX.X	XX.X	XX.X	XX.X
	Range	XX, XX	XX, XX	XX, XX	XX, XX
Week 1	n	X	X	X	X
	Mean (SD)	XX.X (XX.XX)	XX.X (XX.XX)	XX.X (XX.XX)	XX.X (XX.XX)
	Median	XX.X	XX.X	XX.X	XX.X
	Range	XX, XX	XX, XX	XX, XX	XX, XX

*Subjects used their own usual brand cigarettes at Week -1.
VLN non-mentholated = Non-mentholated VLN cigarettes
VLN mentholated = Mentholated VLN cigarettes
UB non-mentholated = Subjects' UB non-mentholated filtered cigarettes
UB mentholated = Subjects' UB mentholated filtered cigarettes

Source: Table 14.2.1.1.1.1
Program: /CAXXXX/sas prg/stsas/intexttest/t_dem.sas DDMMYYYY HH:MM

Programmer Note: All study weeks will be presented in the table.

In-text Table 11-3 will be in the following format:

Table 11-3 Statistical Comparison of Number of Cigarettes Smoked per Week at Weeks 2 and 6 Versus Week -1 by Study Product Group (PP Population)

Study Week	Product Group	Means		Difference (Test Week – Baseline)	XX% Confidence Interval	p-value
		Test Week	Baseline			
Week 2	VLN Non- Mentholated	XXX	XXX	XXX	XXX - XXX	X.XXXX
	VLN Mentholated	XXX	XXX	XXX	XXX - XXX	X.XXXX
	VLN Combined	XXX	XXX	XXX	XXX - XXX	X.XXXX
Week 6	VLN Non- Mentholated	XXX	XXX	XXX	XXX - XXX	X.XXXX
	VLN Mentholated	XXX	XXX	XXX	XXX - XXX	X.XXXX
	VLN Combined	XXX	XXX	XXX	XXX - XXX	X.XXXX

Baseline = Week -1
Subjects used their own usual brand cigarettes at Week -1.

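### SAP 7.3 names two primary analyses of cigarette consumption with different comparators and no order, and the only in-text test is the uncontrolled one

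*SAP*

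**What the plan says.** SAP 7.3 sets out two analyses of consumption and topography. The first is a paired t-test of Week 2 and Week 6 against Week -1, in the two VLN flavour groups and in both pooled. It ends: "The primary analysis will be based on the VLN combined product group". The second is a mixed model for change from baseline with VLN-versus-UB contrasts at Weeks 2 and 6. It ends: "The primary analysis will be the pairwise comparisons of VLN combined versus UB combined (pooled non-mentholated and mentholated groups").

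Protocol 6.1.1 ranks the two differently. On the size of the VLN groups it says "This is based on powering the primary objective of a within-group comparison of cigarette consumption at baseline and end-of-study"; on the smaller UB groups it says "This will provide sufficient power for the secondary objective of between-group comparisons in cigarette consumption". SAP 4.1 repeats both statements. Protocol 6.3.7 introduces the mixed model as an addition: "In addition, a linear mixed model analysis of variance will be used to compare the between-cohort differences". SAP 12 says: "The analyses described in this SAP are aligned with those analyses described in the protocol".

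On reporting, SAP 13.1 lists one in-text statistical comparison of consumption, Table 11-3: "Statistical Comparison of Number of Cigarettes Smoked per Week at Weeks 2 and 6 Versus Week -1 by Study Product Group". Its shell in SAP 14.1 has rows for VLN non-mentholated, VLN mentholated and VLN combined, and none for UB. The VLN-versus-UB comparison of consumption is Table 14.2.1.1.3, listed in SAP 13.2 for Section 14 of the report.

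**The concern.** The two analyses answer different questions. The paired test asks whether VLN subjects smoke less than in their own Week -1. The mixed-model contrast asks whether their change differs from that of smokers followed in the same way who kept their usual brand. The hypothesis (Protocol 1.3, SAP 2.2) concerns what happens on switching to VLN, and only the second analysis removes a change that would have occurred without the switch.

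All subjects keep a daily diary, collect butts and attend repeated clinic visits in an open-label study. If smoking moves further after Week -1 for reasons unrelated to the cigarette, the paired test counts that movement as change after switching. The UB arm can subtract it, but the test that uses the UB arm is not in the body of the report.

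With two analyses called primary and no order between them, the plan also does not say which result decides whether the consumption hypothesis is met.

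**Working it through.** **1. Ranking, side by side**

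| Place | Paired change within VLN | VLN versus UB |
|---|---|---|
| Protocol 6.1.1 | primary objective | secondary objective |
| SAP 4.1 | primary objective | secondary objective |
| Protocol 6.3.7 | main method | additional |
| SAP 7.3 | primary (pooled VLN) | primary (pooled VLN versus pooled UB) |
| SAP 12 | no change declared | no change declared |

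The SAP 7.3 entry for VLN versus UB agrees with none of the other ranking statements. No text gives an order, splits alpha, or chooses between Weeks 2 and 6.

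**2. Reporting, side by side**

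| Output | Placement | UB shown? | Test? |
|---|---|---|---|
| Table 11-2, Figure 11-1 | in-text | yes | no |
| Table 11-3 | in-text | no | paired |
| Table 14.2.1.1.2 (source of 11-3) | post-text | yes | paired |
| Table 14.2.1.1.3 | post-text | yes | VLN versus UB |

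The in-text shells for other endpoints (11-5, 11-7, 11-23) include UB rows. The in-text list has no between-group comparison table for any endpoint.

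**3. The plan's own sample size**

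Inputs: 50 per VLN group, 3 CPD, 80% power, alpha 0.05 (Protocol 6.1.1, two-tailed; SAP 4.1, one-tailed). No SD is given, so the figure of 50 can be neither reproduced nor refuted. The SD it implies comes from solving the paired-t power (noncentral t, n - 1 df, noncentrality 3 × √n / SD) for 80%:

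- n = 50, two-sided: SD = 7.42 CPD
- n = 50, one-sided: SD = 8.41 CPD
- n = 30, two-sided: SD = 5.67 CPD. Thirty pairs is an assumption, standing for a plan that enrols 50 to allow for non-compliance.

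**4. Paired test under a shared drift and no VLN effect**

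Assumptions: SD 5.67-7.42 CPD and 80-100 evaluable VLN subjects out of 100 (2 × 50). Noncentrality = drift × √n / SD. For 1 CPD this is √80 / 7.42 = 1.21 at one end and √100 / 5.67 = 1.76 at the other, against critical values of 1.99 and 1.98. Probability of a significant paired test, two-sided 0.05:

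| Shared drift | SD 7.42, n = 80 | SD 5.67, n = 100 |
|---|---|---|
| 1 CPD | 22% | 42% |
| 1.5 CPD | 43% | 75% |
| 2 CPD | 66% | 94% |

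With 60 evaluable subjects and SD 7.42-8.41 the figures fall to 15-18% at 1 CPD and 44-54% at 2 CPD. In simulation (100 versus 40, SD 7.4, drift 1 or 2 CPD in both arms) the VLN-versus-UB test stayed at about 5%.

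**5. Two primaries, no drift, no effect**

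The two statistics share the VLN data. With equal SDs, 100 versus 40, their correlation is √[(1/100) / (1/100 + 1/40)] = √(0.010 / 0.035) = 0.53. Independent tests would give 1 - 0.95² = 9.75%. At this correlation, simulation gives about 9% for at least one significant result at a single week. Testing at both weeks would add to that; I have not quantified it.

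**6. Power if the between-group contrast is the single primary**

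SE = SD × √(1/100 + 1/40) = SD × 0.187. For 3 CPD, two-sided 0.05, equal SDs:

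- SD 5.67: SE 1.06, noncentrality 2.83, power 80%
- SD 7.42: SE 1.39, noncentrality 2.16, power 57%
- SD 7.42 in VLN and half that in UB: power 88%

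The corresponding paired SE with 100 subjects is SD / 10.

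**The case against.** The strongest reply is that each sentence in SAP 7.3 only selects the pooled contrast over the flavour-specific ones within its own method. SAP 4.1 already ranks within-group first, and the mixed model is introduced as an addition. On that reading the clash is loose wording and SAP 12 is not contradicted. This softens the point but does not remove it: two pooled tests still carry the primary label at 0.05, and SAP 7.3 does not say which one decides.

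A reader might infer that the in-text consumption results carry no control at all, so that a drift would be reported as the VLN effect. The documents do not support that. Table 11-2 has UB columns beside VLN for every study week, and Figure 11-1 is by product group, so a movement in UB would be visible. The controlled test is prespecified and tabulated. Protocol 6.3 plans within-group comparisons for all groups, and SAP 14 warns that shells may not reflect every aspect of the study, so the missing UB rows in Table 11-3 may be a slip. A reader might also infer that the sponsor would headline whichever test succeeds; nothing in the documents shows such an intention.

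The drift argument has limits. Diary and butt collection start at the beginning of Week -1, so baseline is already measured under observation and only further change biases the paired test. The documents give no drift size, no SD and no evaluable number, and the PP exclusions could leave fewer than 80. Nor is the between-group contrast immune: the cotinine rule for PP membership applies after switching and so selects differently by arm, VLN cigarettes are supplied while UB subjects buy their own, and the study is open-label.

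Finally, the stated objective is to characterise behaviour around the switch, and 50 per group was set for the paired test. Keeping that test primary is therefore a legitimate choice, provided the plan says so.

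**Conclusion.** The point holds as an unresolved ranking and a reporting gap. SAP 7.3 gives two analyses with different comparators the primary label without an order or a primary week, against the ranking in Protocol 6.1.1 and SAP 4.1 and the alignment statement in SAP 12. The only in-text test of consumption cannot separate a VLN effect from change common to both arms; the test that can is post-text.

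Misreading a shared change as a VLN effect is a risk, not a certainty. Its size is illustrative: 22-42% for a 1 CPD shared fall, given SD 5.7-7.4 CPD and 80-100 evaluable subjects, and less with a larger SD or fewer PP subjects. The figure of about 9% for either primary under the null assumes 100 versus 40, equal SDs and one week. The plan should be changed, though the controlled analysis already exists in it.

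**What to change.** In SAP 7.3, name one primary contrast for consumption and one primary week, Week 6, and label the other analysis and Week 2 supportive.

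- **Preferred for any claim that VLN reduces consumption:** change in CPD from Week -1 to Week 6, VLN combined versus UB combined. This alters the protocol's ranking, so amend Protocol 6.1.1 and 6.3.7 (Protocol 6 asks for an amendment when the primary analysis changes in a major way), revise SAP 4.1, and record the change in SAP 12. Restate the power with the sponsor's own SD.
- **If the paired test stays primary:** relabel the mixed-model contrast secondary in SAP 7.3, in line with Protocol 6.1.1 and SAP 4.1.

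In either case, move Table 14.2.1.1.3 in-text beside Table 11-3 and add the UB rows to Table 11-3. Limit any between-group primary to consumption: topography is measured only in subjects assigned to VLN (Protocol 5.12.5, SAP 7.1.3), so that contrast cannot be estimated there.

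The cost is SAP wording, table placement and, for the preferred option, a short amendment; the contrasts are already planned. The real downside of the preferred option is a wider interval and lower, SD-dependent power for 3 CPD: about 80% at SD 5.67 but 57% at SD 7.42 with 100 versus 40 and equal SDs.
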